6.2 IMPORTANT PROTOCOL VIOLATION

Data discrepancies and deviations from the CTP will be identified for all subjects in the database (i.e., treated subjects and subjects with SAEs which the investigator considered related to the screening procedure). Consistency check listings (for identification of violations of time windows) and a list of protocol deviations (e.g. deviations in drug administration, in blood sampling times, etc.) will be provided to be discussed at the combined blinded report planning meeting (BRPM) and database lock meeting (DBLM). At this meeting, it will be decided whether the discrepant data value can be used in analysis or whether it must be corrected in the clinical database. Each protocol deviation must be assessed to determine whether it is an important protocol violation (PV). For definition of important PVs, and for the process of identification of these, refer to the Boehringer Ingelheim (BI) reference document "Protocol Violation Handling Definitions" ([3](#)).

If any important PVs are identified, they are to be summarised into categories and will be captured in the BRPM/DBLM minutes via an accompanying Excel spreadsheet ([2](#)). The following table contains the categories which are considered to be important PVs in this trial. If the data show other important PVs, this table will be supplemented accordingly by the time of the BRPM/DBLM.

Category /Code	Description	Identification

[figure not shown]
¹ Time deviations will only be flagged as important PV, when leading to exclusion of the entire subject from an analysis set
Source: 'Protocol Violation Handling Definitions' [001-MCS-50-413_RD-01] (3)

6.3 SUBJECT SETS ANALYSED

All subjects who received study medication will be included in the safety analysis and in the analysis of pharmacodynamic (PD) and PK endpoints depending on the availability of measurement values, and on their adherence to the CTP.

The following analysis sets will be defined for this trial:

- **Enrolled set (ES)**
This subject set includes all subjects who were screened for inclusion into the study, i.e., who were assigned a subject number.
It will be used for analyses of subject disposition.
- **Randomised set (RS):**
This subject set includes all randomised subjects, i.e., who were assigned a randomisation number, whether treated or not.
It will be used for analyses of subject disposition.
- **Treated set (TS):**
This subject set includes all subjects in the RS who received at least one dose of study drug. This is the full analysis set population in the sense of ICH-E9.
It will be used for analysis of safety, demographic data and baseline characteristics.

- Pharmacodynamic set (PDS):
This subject set includes all subjects in the TS who have evaluable cell counts measured after 24 hours of the segmental challenge in primary, secondary or further endpoints related to BAL assessment. Whether a subject has evaluable cell counts will be decided no later than in the BRPM (cf. CTP Section 7.3).

The discussion of all exceptional cases and problems and the decisions on the allocation of subjects to populations will be made at latest at the BRPM/DBLM.

Table 6.3: 1 Subject sets analysed

Class of endpoint	Analysis set						
	ES	RS	TS	[REDACTED]	[REDACTED]	PDS	[REDACTED]
Primary and secondary endpoints and further endpoints related to BAL assessment which were measured after 24 hours of the segmental challenge						X	
[REDACTED]							
Safety endpoints			X				
Demographic/baseline endpoints			X				
Important PVs		X					
Disposition	X	X					
[REDACTED]							

6.5 POOLING OF CENTRES

This section is not applicable, because the study was performed in only one centre.

6.6 HANDLING OF MISSING DATA AND OUTLIERS

The endpoints will be used as defined in the CTP, Section 7.4.

CTP: Missing safety and pharmacodynamic data will not be imputed.

[figure not shown]
Missing or incomplete AE dates are imputed according to BI standards (see 001-MCG-156_RD-01 (4)).

6.7 BASELINE, TIME WINDOWS AND CALCULATED VISITS

In general, baseline is defined as the last measurement before first trial medication intake at Visit 2. This applies e.g. to laboratory data, vital signs, body weight, and pulmonary function testing, exceptions are BAL assessments 

For endpoints related to BAL assessments, baseline is defined as the measurement at Visit 6.

Time windows are defined in Section 6.1 of the CTP. Adherence to time windows will be checked via the consistency check listings at the BRPM/DBLM.

[figure not shown]
7. PLANNED ANALYSIS

The format of the listings and tables will follow the BI guideline "Reporting of clinical trials and project summaries" (001-MCG-159) (6).

The individual values of all subjects will be listed, sorted by treatment group, subject number and visit (if visit is applicable in the respective listing). AE listings will be sorted by assigned treatment (see [Section 7.8.1](#) below for details). The listings will be contained in Appendix 16.2 (SDL) of the CTR.

The following standard descriptive statistical parameters will be displayed in summary tables of continuous variables:

N	number of non-missing observations
Mean	arithmetic mean
SD	standard deviation
Min	minimum
Median	median
Max	maximum

Tabulations of frequencies for categorical data will include all possible categories and will display the number of observations in a category as well as the percentage (%) relative to the respective treatment group. Percentages will be rounded to one decimal place. The category missing will be displayed if and only if there are actually missing values. Percentages will be based on all subjects in the respective subject set whether they have non-missing values or not.

7.1 DEMOGRAPHIC AND OTHER BASELINE CHARACTERISTICS

Only descriptive statistics are planned for this section of the CTR, based on the TS.

The data will be summarised for each treatment group and in total.

7.2 CONCOMITANT DISEASES AND MEDICATION

Frequency tables are planned for this section of the CTR, based on the TS.

Concomitant diseases will be coded using the coding system of the Medical Dictionary for Drug Regulatory Activities (MedDRA). Medications will be coded using the World Health Organization Drug Dictionary (WHO-DD). The coding version number will be displayed as a footnote in the respective output.

The diagnoses and medications will be listed. Subjects without any concomitant diagnoses or concomitant therapies should be marked with a “No” in the respective column.

The relevance of the concomitant therapies to the evaluation of [REDACTED] PD will be decided no later than at the BRPM/DBLM.

7.4 PRIMARY ENDPOINT

As described in CTP Section 7.3.1, the primary analysis of the primary endpoint will be an analysis of variance (ANOVA) on the log-transformed scale, based on the PDS. The ANOVA model is described in CTP Section 7.1.3.

As described in CTP Section 7.2, the primary endpoint is subject of a confirmatory statistical hypothesis test, based on the primary analysis:

[figure not shown]
H_0 : geometric mean ratio, i.e. T/R, of the primary endpoint is 1.

H_a : geometric mean ratio, i.e. T/R, of the primary endpoint is not equal to 1.

H_0 will be rejected if its p-value is ≤ 0.1 .

H_a is a two-sided alternative hypothesis; testing this hypothesis at the 10% significance level is equivalent to using two one-sided tests, each at the 5% significance level.

No other confirmatory statistical hypothesis tests will be conducted in this trial.

Descriptive statistics and boxplots of the primary endpoint by treatment will also be provided.

7.5 SECONDARY ENDPOINTS

7.5.1 Key secondary endpoints

This section is not applicable as no key secondary endpoint has been specified in the CTP.

7.5.2 Secondary endpoints

As described in CTP Section 7.3.2, secondary endpoints will be statistically assessed using the same methods as described for the primary analysis of the primary endpoint, based on the PDS.

No confirmatory statistical hypothesis tests will be conducted based on the secondary endpoints.

Descriptive statistics and boxplots of the secondary endpoints by treatment will also be provided.

[figure not shown]

7.6.3 Endpoints related to safety assessments

These endpoints will be analysed based on the TS.

For analysis related to AEs, refer to [Section 7.8.1](#).

CTP: *For weight the measurements per time point and the difference from baseline for the on-treatment measurements will be analyzed descriptively.*

7.8 SAFETY ANALYSIS

All safety analyses will be performed on the TS.

If not stated otherwise, the safety results will be sorted by actual treatment.

Data of screened subjects, who withdrew after screening examination but prior to treatment, will not be included in the CTR. Exceptions are screen-failed subjects who had an SAE after the screening period, which was considered by the investigator to be related to the screening procedure. The safety data for treated subjects who failed to complete the study (dropouts or withdrawals) will be reported as far as their data are available. All withdrawals will be documented and the reason for withdrawal recorded.

7.8.1 Adverse events

AEs will be coded with the most recent version of MedDRA.

The analyses of AEs will be descriptive in nature. All analyses of AEs will be based on the number of subjects with AEs and not on the number of AEs.

For analysis, multiple AE occurrence data on the eCRF will be collapsed into one event provided that all of the following applies:

- All AE attributes are identical (lower level term, intensity, action taken, therapy required, seriousness, reason for seriousness, relationship, outcome, AESI)
- The occurrences were time-overlapping or time-adjacent (time-adjacency of 2 occurrences is given if the later occurrence started at most 1 hour after the first occurrence ended).

For further details on summarization of AE data, please refer to 'Handling and summarization of AE data for clinical trial reports and integrated summaries' (8) [001-MCG-156] and "Handling of missing and incomplete AE dates" (4) [001-MCG-156_RD-01].

The analysis of AEs will be based on the concept of TEAEs. That means that all AEs will be assigned to the treatment, post-treatment, screening or post-study phases as defined in [Section 6.1](#).

An overall summary of AEs will be presented. This overall summary will comprise summary statistics for the class of other significant AEs according to ICH E3 and for the class of AESIs.

CTP: *The following are considered as AESIs:*

Hepatic injury

A hepatic injury is defined by the following alterations of hepatic laboratory parameters:

- *an elevation of AST and/or ALT > 3 fold upper limit normal (ULN) combined with an elevation of total bilirubin > 2 fold ULN measured in the same blood draw sample, and/or*
- *marked peak aminotransferase (ALT and/or AST) elevations ≥ 10 fold ULN*

The investigator had to classify in the eCRF whether an observed AE was an AESI or not.

According to ICH E3 (9), AEs classified as ‘other significant’ need to be reported and will include those non-serious and non-significant AEs with

- (i) ‘action taken = discontinuation’ or ‘action taken = reduced’, or
- (ii) marked haematological and other lab abnormalities or AEs which lead to significant concomitant therapy as identified by the Clinical Monitor/Investigator at the BRPM.

The frequency of subjects with AEs will be summarised by treatment, primary system organ class and preferred term. This summary table will be shown based on all reported AEs. Furthermore separate tables will be presented for the frequency of subjects with procedural on-treatment AEs, the frequency of subjects with LPS related on-treatment AEs, and the frequency of subjects with non-procedural and non-LPS-related on-treatment AEs. AEs which were considered by the investigator to be related to the investigational study drug will be summarised separately. Separate tables will be provided for subjects with SAEs, subjects with AESIs and subjects with other significant AEs (according to ICH E3 (9)). AEs will also be summarised by maximum intensity.

The system organ classes will be sorted according to the standard sort order specified by the European Medicines Agency (EMA), preferred terms will be sorted by total frequency (within system organ class). The MedDRA version number will be displayed as a footnote in the respective output.

In addition, frequencies of subjects with non-serious AEs that had an incidence of > 5% (in preferred terms) for at least one treatment will be summarised by treatment, primary system organ class and preferred term.

For disclosure of AE data in the European Union Drug Regulating Authorities Clinical Trials (EudraCT) register, additional information not included in a standard AE analysis will be performed. The following three entries will be created:

- AEs per arm for disclosure on EudraCT
- Non-serious AEs for disclosure on EudraCT
- Serious AEs for disclosure on EudraCT

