#### Hepatic injury

A hepatic injury is defined by the following alterations of hepatic laboratory parameters:

- an elevation of AST and/or ALT  $\geq 3$  fold upper limit normal (ULN) combined with an elevation of total bilirubin  $\geq 2$  fold ULN measured in the same blood draw sample, and/or
- marked peak aminotransferase (ALT and/or AST) elevations  $\geq 10$  fold ULN

These lab findings constitute a hepatic injury alert and the subjects showing these lab abnormalities need to be followed according to the "DILI checklist" provided via the RDC system.

In case clinical symptoms of hepatic injury (for example, icterus, unexplained encephalopathy, unexplained coagulopathy, right upper quadrant abdominal pain) without available lab results (ALT, AST, total bilirubin), the investigator should make sure these parameters are analyzed, if necessary in an unscheduled blood test. Should the results meet the criteria of hepatic injury, the procedures described in the DILI checklist should be followed.

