7.8.2 Laboratory data

The analyses of laboratory data will be descriptive in nature and will be based on BI standards (10). If possible, analyses will be based on original values. If multiple reference ranges apply for a parameter (e.g. due to different age groups), analyses will be based on normalised values, which means transforming to a standard unit and a standard reference range.

Descriptive statistics of laboratory values over time and for the difference from baseline (see Section 6.7, for on-treatment measurements) will be provided. Frequency tables of changes between baseline and last value on treatment with respect to the reference range will be presented.

CTP: *Values outside the reference range as well as values defined as clinically relevant will be highlighted in the listings.*

Urine dipstick data will neither be listed nor analysed.

Clinically relevant abnormal findings in laboratory data as judged by investigator will be reported as AEs (CTP Section 5.3.3) and will be analysed as part of AE analysis. Standard or project-specific rules for flagging clinically significant values will not be applied in this study.

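### Hepatic-injury AESI: the SAP and protocol thresholds differ in sign as extracted and, separately, the visible SAP relies on the investigator's flag with no stated laboratory cross-check

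*SAP*

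**What the plan says.** **Definition.** Protocol 5.3.6.1 (Hepatic injury) has two laboratory criteria. The first is "an elevation of AST and/or ALT $\geq 3$ fold upper limit normal (ULN"), joined to bilirubin as "fold upper limit normal (ULN) combined with an elevation of total bilirubin $\geq 2$ fold ULN measured in the same blood draw sample". The second is ALT and/or AST at or above 10 times ULN. Values meeting either are a hepatic injury alert, with follow-up by the DILI checklist.

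SAP 7.8.1 restates this under a label that marks it as protocol text. Its first criterion reads "an elevation of AST and/or ALT > 3 fold upper limit normal (ULN) combined with an elevation of total bilirubin > 2 fold ULN"; its second reads "marked peak aminotransferase (ALT and/or AST) elevations ≥ 10 fold ULN". SAP Section 4, which lists changes to the planned analysis, mentions no change to the AESI definition.

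**Identification.** SAP 7.8.1: "The investigator had to classify in the eCRF whether an observed AE was an AESI or not". On output, the same section says: "Separate tables will be provided for subjects with SAEs, subjects with AESIs and subjects with other significant AEs".

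**Laboratory data.** SAP 7.8.2 plans descriptive statistics over time, tables of change from baseline to the last on-treatment value against the reference range, and listings with out-of-range values highlighted. It adds: "Standard or project-specific rules for flagging clinically significant values will not be applied in this study".

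**The concern.** There are two points, and they are independent.

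1. Two signs in a passage presented as protocol text do not match the protocol. A programmer working from the SAP and an investigator working from the protocol could classify a value exactly at a threshold differently.

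2. The event is defined by laboratory numbers, but the visible route into the AESI table is a chain of human steps. The value is reported as an AE (protocol 5.3.3.1 ties this to the investigator's judgement of clinical relevance), and that AE is then classified as an AESI. No visible text compares the result with the laboratory data. If a step fails, the table of the one visible AESI is incomplete and no planned output is designed to reveal it.

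**Working it through.** **Step 1: how far the two wordings differ.** Let a be the higher of ALT and AST, and b total bilirubin from the same draw, both in multiples of ULN.

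- Protocol rule: (a ≥ 3 and b ≥ 2) or a ≥ 10
- SAP rule as extracted: (a > 3 and b > 2) or a ≥ 10

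| a | b = 1.9 | b = 2.0 | b = 2.1 |
|---|---|---|---|
| 2.9 | neither | neither | neither |
| 3.0 | neither | **protocol only** | **protocol only** |
| 3.1 | neither | **protocol only** | both |
| 9.9 | neither | **protocol only** | both |
| 10.0 | both | both | both |

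The rules part only when a is below 10, the protocol rule is met, and either a is exactly 3 or b is exactly 2. With matching signs no cell differs. No planned AESI count would change either, because the visible SAP describes no programmed use of these thresholds.

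**Step 2: what a qualifying but unflagged case would look like.** The Flow Chart schedules safety blood tests at Visits 1, 2, 4, 6, 7 and 8. Take a subject with a = 3.1 and b = 2.1 at Visit 4 (meeting both wordings), back in range by the last on-treatment draw, with no AESI flag.

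| Planned output | What it shows |
|---|---|
| AESI table (SAP 7.8.1) | Nothing |
| Statistics over time (SAP 7.8.2; the maximum is a standard statistic in Section 7) | High maxima, separately per parameter; not that they belong to one draw |
| Shift table (SAP 7.8.2) | Nothing, since it uses the last on-treatment value; it also uses the reference range, not multiples of ULN |
| Listings (SAP 7.8.2) | Each value highlighted as out of range; the reader must combine them |
| Other significant AEs (SAP 7.8.1) | Only if picked out by hand at the blinded report planning meeting, and then in a different table |

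The values stay in the report, but no visible output tests the joint same-draw criterion or compares it with the flag.

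**Step 3: size.** One missed case in an arm of 25 is 1/25 = 4%. This is the weight of a single case, not an estimate of how likely one is. A programmed check would cover about 6 × 50 = 300 scheduled draws if all 50 subjects completed every visit, plus any unscheduled ones.

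**The case against.** **The sign difference may be an extraction effect.** Both differing signs sit in one bullet, and an underlined sign can lose its underline while a true at-or-above character survives elsewhere. The next bullet keeps its sign, which makes this less likely but does not exclude it. So the documents do not support calling it a misquotation until the SAP page has been seen.

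**A reader might infer that the stricter signs cause cases to be missed.** They do not. If AESIs come from the investigator's flag, the SAP wording is never applied to data, and the investigator works from the protocol. The risk of an incomplete table comes from reliance on the flag alone.

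**A reader might also infer that nothing checks these values.** That is too strong. The investigator must evaluate every laboratory report (protocol 5.3.3.1). A qualifying value triggers the DILI checklist, and an AESI must be reported within 24 hours (5.3.6.1, 5.3.7). Data discrepancies go to the combined blinded report planning and database lock meeting (SAP 6.2). An unflagged case therefore requires a lapse in protocol duties. This makes it unlikely, but these safeguards are not a comparison of the laboratory criterion with the flag.

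**The absence is inferred from silence.** Nearby SAP text is redacted, and the cited sponsor guidelines on AE and laboratory analysis and the analysis data set plan are not available. A reconciliation may be described there. This stands as a limit on the point.

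**The protocol requires no programmed check.** True in the visible text, and safety is purely descriptive. The change is an improvement, not the repair of a contradiction.

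**Conclusion.** Both points hold in limited form and are of low priority.

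1. As extracted, the SAP and protocol disagree in two of three threshold signs and must be reconciled once the SAP page has been checked. The effect is confined to values exactly at a threshold, and arises only if the SAP wording were programmed. No view is taken on which threshold is clinically right.

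2. On the visible text, a qualifying case that the investigator did not flag would be absent from the AESI table, though its values would remain in the laboratory summaries and listings. Such cases should be rare.

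The second point assumes that no cross-check stands in the redacted text or in the unavailable sponsor documents. It also assumes that AST, ALT and total bilirubin are held per draw in the database. The protocol's laboratory parameter table is not visible, but SAP 5.4.5.3 leaves out only urine dipstick data.

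**What to change.** - Check the SAP page and reconcile the hepatic-injury text in SAP 7.8.1 with protocol 5.3.6.1. If a difference is intended, record it in SAP Section 4.
- Derive the reconciled criterion by program from AST, ALT and total bilirubin of the same blood draw, together with the separate 10-fold criterion.
- List every subject who meets it, whether flagged or not, and bring that list to the combined blinded report planning and database lock meeting. Resolve any mismatch with the investigator's flag before lock.
- If a sponsor guideline already requires this reconciliation, a cross-reference in SAP 7.8.1 is enough.

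Cost: one corrected bullet, a few lines of programming on blood results already collected, and possibly some extra queries to the site.

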### 3. DESCRIPTION OF DESIGN AND TRIAL POPULATION

#### 3.1 OVERALL TRIAL DESIGN AND PLAN

An overview of the trial design is shown in Figure 3.1.1.

[figure not shown]

Figure 3.1.1: Study Design

This is a randomized, double-blind, placebo-controlled, parallel-group, single center study to assess the proof of mechanism and safety of BI 1026706 compared to placebo. The respective treatment will be administered orally as tablet twice daily during the 4 week treatment period. The random allocation to active or placebo treatment will have a ratio of 1:1.

A total of 50 subjects will participate in the trial consisting of 2 treatment groups of 25 subjects, each treated for 28 ± 2 days.

This trial consists of 8 Visits. Visit 1 is the screening visit. Between Visits 2-6 subjects will receive either BI 1026706 or placebo for 28 ± 2 days, depending on the treatment group they have been randomized to. In addition, at Visit 6 baseline BAL will be conducted following LPS and saline challenge. At Visit 7 the BAL will be examined for the 24 hours post LPS and saline challenge. Visit 8 is the end-of-trial examination.

The screening period lasts from the signature of informed consent at Visit 1 until randomization (directly followed by first administration of trial medication) on Day 1 (Visit 2).

The screening visit (Visit 1) will take place 3 to 28 days prior to randomization.

The treatment period lasts from the first administration of trial medication on Day 1 (Visit 2) until Day 28 ± 2 days (Visit 6).

The follow-up period lasts from Day 29 (Visit 7) until the End of trial (Day 32 to 34, Visit 8).

Please refer to [Section 8.6](#) for the definition of the end of trial.

Subjects are included in the study once they have signed the informed consent and their participation concludes when they have undergone the last planned visit. The end of trial visit (Visit 8) also needs to be completed if the subject withdraws from or is removed from the trial following randomization ([see Section 3.3.3](#))

All trial relevant documentation will be stored by Boehringer Ingelheim in the Trial Master File (TMF). Trial relevant documentation for the study sites will be filed in the Investigator Site File (ISF).

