### 3.1.1 Administrative structure of the trial

Boehringer Ingelheim has appointed a Trial Clinical Monitor, responsible for coordinating all required activities, in order to manage the trial in accordance with applicable regulations and internal standard operating procedures (SOPs), direct the clinical trial team in the preparation, conduct, and reporting of the trial, order the materials as needed for the trial, and ensure appropriate training and information of local clinical monitors (CML), Clinical Research Associates (CRAs), and investigators of participating countries. Data Management and Statistical Evaluation will be done by BI according to BI SOPs.

Tasks and functions assigned in order to organize, manage, and evaluate the trial will be defined according to BI SOPs. A list of responsible persons and relevant local information can be found in the ISF.

Relevant documentation on the participating (Principal) Investigators and other important participants, including their *curricula vitae*, will be filed in ISF.

The study will be conducted at a clinical research center [REDACTED] specialized on pulmonary diseases, and experienced in the management of healthy volunteers and patients with respiratory diseases. The Principal Investigator is an expert in the respiratory therapy area.

A local laboratory facility will handle all laboratory analyses of the trial. Lung function assessment (spirometry) will be performed with site's own equipment according to international accepted guidelines.

Safety status will be assessed by clinical laboratory tests, vital signs, physical examination, electrocardiogram (ECG), and monitoring of adverse events. As a further safety measure, the pulmonary function will be examined by spirometry according to [Flowchart](#).

Bronchoscopies and medical checks (including spirometry) prior to discharge of subject will be performed according to the Fraunhofer Institute study site standard operating procedure (provided in the ISF), which is based on guidelines for investigative bronchoscopies.

On the last day of treatment (Visit 6), subjects undergo bronchoscopy with BAL and segmental instillation of endotoxin and saline (control), each in different segments of contralateral lungs. Twenty-four hours later (Visit 7), subjects undergo a second bronchoscopy for the collection of BAL fluid from both challenged segments. BAL fluid from both days will be processed and total and differential cell counts will be determined.

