#### 7.3.4 Safety analyses

Safety will be assessed for the further endpoints listed in [Section 5.1.3](#) as well as the further safety assessments described in [Section 5.3](#). All treated subjects (that is, all subjects who received at least one dose of study drug), will be included in the safety evaluation. Safety analyses will be descriptive in nature and will be based on BI guideline ‘Analysis and presentation of adverse event data from clinical trials’ (001-MCG-156).

The analyses will be done by ‘treatment at onset’.

Tabulations of frequencies/proportions will be used for the evaluation of categorical (qualitative) data, and tabulations of descriptive statistics will be used to analyze continuous (quantitative) data.

Measurements (such as ECG, vital signs, or laboratory parameters) or AEs will be assigned to treatments (see [Section 4.1](#)) based on the actual treatment at the planned time of the measurement or on the recorded time of AE onset (concept of treatment emergent AEs).

[figure not shown]
Therefore, measurements planned or AEs recorded prior to first intake of trial medication will be assigned to 'screening', those between first trial medication intake until the end of the REP will be assigned to ‘on-treatment’, and those between end of REP and end-of-trial examination will be assigned to ‘post-treatment’ and those after the end of trial examination will be assigned to ‘post-study’. These assignments including the corresponding time intervals will be defined in detail in the TSAP.

Additionally, further treatment intervals (analysing treatments) may be defined in order to provide summary statistics for time intervals, such as combined treatments, on-treatment totals or periods without treatment effects (such as screening and post-study intervals).

[figure not shown]
Adverse events will be coded using the MedDRA. Frequency, intensity and causal relationship of AEs will be tabulated by treatment, primary system organ class and preferred term. SAEs and other significant AEs (according to ICH E3), and AESIs will be listed separately (see [Section 5.3.7](#)).

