Rationale for change		The drop-out rate in the trial after approximately 50% of subjects recruited into the trial is close to the cut-off point for replacement. To allow a seamless recruitment in the trial, replacement of subjects will need to start already prior to reaching the cut-off of maximum numbers of drop-outs. Spare reserve medication at the site will be used for this purpose which will require implementation of a trial-independent site-staff member with restricted access to randomization codes. This dedicated function will instruct the site's trial staff in a blinded manner which medication is to be dispensed to the replacement subjects.

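### LPS-related adverse events are reported as a percentage of everyone dosed, although LPS is given only at Visit 6: add tables with the exposed subjects as denominator

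*SAP*

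**What the plan says.** **Tables.** SAP 7.8.1 plans that "separate tables will be presented for the frequency of subjects with procedural on-treatment AEs, the frequency of subjects with LPS related on-treatment AEs", and a third table for events that are neither procedural nor LPS-related. It states no denominator for any of them.

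**Analysis set.** SAP 7.8 supplies it: "All safety analyses will be performed on the TS". Table 6.3:1 agrees. SAP 6.3 defines the Treated Set (TS): "This subject set includes all subjects in the RS who received at least one dose of study drug". Protocol 7.3.4 uses the same population: "All treated subjects (that is, all subjects who received at least one dose of study drug), will be included in the safety evaluation".

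**Percentages.** SAP 7: "Percentages will be based on all subjects in the respective subject set whether they have non-missing values or not".

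**Timing.** Under Protocol 3.1, the first tablet directly follows randomisation on Day 1. Under Protocol 3.1.1 and the flow chart, the first bronchoscopy and the LPS instillation take place at Visit 6, on Day 28 ± 2.

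**Losses before the challenge.** Protocol 2.3.1 lets the procedures be withheld or stopped after an adverse event judged to be a contraindication. Protocol 3.3.4.1 provides for withdrawal after a respiratory infection that might interfere with bronchoscopy. Protocol 7.7 expects 10% to 20% of neutrophil counts to be unavailable. Protocol 3.3.5 considers replacement once more than 6 subjects do not, or are not expected to, complete. The rationale for global amendment 4 states: "The drop-out rate in the trial after approximately 50% of subjects recruited into the trial is close to the cut-off point for replacement".

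**The concern.** A subject enters the TS with the first tablet but is at risk of an LPS reaction only from Visit 6. A subject who leaves in between cannot have such a reaction, yet counts in the denominator as someone without one. The table therefore answers a different question from the one its title suggests. A reader will take it as the risk of a reaction to the challenge, but it gives the proportion of all dosed subjects who both reached the challenge and reacted.

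The percentage is too low as an estimate of challenge risk as soon as one treated subject goes unchallenged. If the two arms lose different numbers before Visit 6, the arm that loses more will also show the lower percentage at equal underlying risk. In a trial whose benefit-risk section says that active treatment may speed resolution of the LPS-induced inflammation, such a gap could be misread as a drug effect.

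**Working it through.** **The plan's own figures.** The documents give no adverse event rate, so there is none to reproduce. The loss allowance behind the sample size does reproduce: 22 evaluable per arm / 0.90 = 24.4, rounded up to 25 per arm, 50 in total.

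**Formula.** Let x be the number of subjects with an LPS-related event, c the number challenged and n the number in the TS. The planned table shows x/n. The rate among the exposed is x/c. Hence

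reported rate = rate among challenged × (c/n), and the relative shortfall is 1 − c/n.

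The shortfall does not depend on the event rate. The rates of 40% and 20% below are assumptions, used only to show the effect in percentage points.

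**Overall dilution.**

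- 10% unchallenged (lower end of the Protocol 7.7 range): 40% × 0.90 = 36.0%; 20% × 0.90 = 18.0%.
- 12% unchallenged (6 of 50, from the replacement cut-off in Protocol 3.3.5): 40% × 44/50 = 35.2%; 20% × 44/50 = 17.6%.
- 20% unchallenged (upper end of the Protocol 7.7 range): 40% × 0.80 = 32.0%; 20% × 0.80 = 16.0%.

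The 10% and 20% rows are upper limits for the corresponding loss rates, because the protocol's range also counts subjects who were challenged but gave an unusable sample.

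**Replacement does not remove it.** Drop-outs who took a tablet stay in the TS when they are replaced. With 6 drop-outs, all unchallenged and all replaced by subjects who reach the challenge, n = 56 and c = 50. The factor is 50/56 = 0.893, a shortfall of 10.7%.

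**Between arms.** Take 25 per arm, an equal true rate of 40% among challenged subjects, and 6 losses in total before Visit 6. The split is assumed:

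- 3 and 3: 40% × 22/25 = 35.2% in both arms.
- 2 and 4: 40% × 23/25 = 36.8% against 40% × 21/25 = 33.6%.
- 1 and 5: 40% × 24/25 = 38.4% against 40% × 20/25 = 32.0%.
- 0 and 6: 40.0% against 40% × 19/25 = 30.4%, a ratio of 0.76 with no true difference.

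An equal split leaves the comparison undistorted. The gap comes entirely from imbalance.

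**The case against.** **Limited consequence.** Safety is descriptive, no decision rule uses these percentages, and the numerators are correct. Individual values are listed, disposition is reported, and withdrawals are recorded with reasons. A careful reader of the report could work out who reached the challenge. This stands, and it makes the point an inexpensive improvement rather than a serious defect. It does not make the printed percentage the risk of a reaction to LPS.

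**The TS protects the comparison.** Apart from subjects never dosed, the TS keeps the groups as randomised. Receipt of LPS is determined about four weeks later, and adverse events or infections that treatment might influence can prevent it. A comparison restricted to exposed subjects is open to selection. This also stands, and it is the reason to add tables rather than replace the planned ones.

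**Procedural events are wider than bronchoscopy.** A reader might infer that the whole procedural table has the same fault. The documents do not support that. Protocol 2.3.1 lists cannula and venepuncture harms among the procedure risks, and the flow chart has safety bloods at Visits 2 and 4. The readable SAP does not confine the term to bronchoscopy. Subjects who never reach Visit 6 can have procedural events, and limiting that table to bronchoscoped subjects could drop real ones.

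**Unseen source.** SAP 7.8.1 refers further summarisation details to a sponsor guideline that is not available here. An exception there is possible, but the statement in SAP 7.8 covers all safety analyses and names none.

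**Conclusion.** The point holds for LPS-related events, and for bronchoscopy-related events within the procedural group. Read together, SAP 6.3, 7, 7.8 and 7.8.1 report them over all dosed subjects, and the percentage falls short of the exposed-subject rate by the fraction not challenged. The shortfall is 12% in relative terms if 6 of 50 are unchallenged, and at most 10% to 20% on the protocol's planning range. Both rest on assumptions. The replacement cut-off counts non-completers, who may include subjects challenged at Visit 6 and lost before Visit 8. The 10% to 20% is an expectation, not an observed loss.

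Three stronger readings are tempting and go beyond the documents:

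- **A 24% loss.** A reader might set about 6 drop-outs against about 25 recruited at the time of amendment 4. The amendment gives no count. Set against the planned 50, the same cut-off is 12%.
- **A spurious advantage for the drug.** With an assumed 50% event rate and 6 active against 2 placebo losses, the table would show 50% × 19/25 = 38% against 50% × 23/25 = 46%. Neither the rate nor the split is in the documents. Distortion between arms is possible, but neither its presence nor its direction is established.
- **That this hides the trial's main hazard.** The documents do not rank the hazards, and Protocol 2.3.1 describes LPS instillation at the chosen dose as generally well tolerated.

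**What to change.** In SAP 7.8.1, with the two sets defined in 6.3:

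- Keep all planned TS tables.
- Add an LPS-related on-treatment AE table whose denominator is treated subjects who received the LPS instillation.
- Add a bronchoscopy-related on-treatment AE table whose denominator is treated subjects who had at least one bronchoscopy. Keep other procedural events, such as those from blood sampling, on the TS.
- Show the number exposed per arm in the column headers.
- Add a footnote that these sets are formed after randomisation, so comparisons between arms within them are descriptive and open to selection.

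The cost is some SAP wording, two population flags and two extra tables on a smaller, post-randomisation subset. The flags should need no new data: Protocol 7.3 already has conduct of the LPS administration reviewed for evaluability, and SAP 7.9.1 lists the start date and time of each bronchoscopy.
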